#### **4.5.3 Patient Discontinuation**

The investigator has the right to discontinue a patient from study drug or withdraw a patient from the study at any time. In addition, patients have the right to voluntarily discontinue study drug or withdraw from the study at any time for any reason. Reasons for discontinuation of study drug or withdrawal from the study may include but are not limited to the following:

- Patient withdrawal of consent at any time
- Any medical condition that the investigator or Sponsor determines may jeopardize the patient's safety if he or she continues in the study
- Investigator or Sponsor determines it is in the best interest of the patient.
- Patient non-compliance, specifically defined as patient's refusal to take the required doses of study drugs, unless for a reason, as defined below

In cases where the patient decides to prematurely discontinue study treatment ("refuses treatment"), he or she should be asked if he or she can still be contacted for further information. The outcome of that discussion should be documented in both the medical records and in the eCRF. If the patient is lost to follow-up, the investigator should contact the patient or a responsible relative by telephone followed by registered mail to establish the reason for the withdrawal as completely as possible. A complete final evaluation at the time of the patient's withdrawal should be made with an explanation of why the patient is withdrawing from the study.

When applicable, patients should be informed of circumstances under which their participation may be terminated by the investigator without the patient's consent. The investigator may withdraw patients from the study in the event of intercurrent illness,

adverse events, treatment failure after a prescribed procedure, lack of compliance with the study and/or study procedures (e.g., dosing instructions, study visits), cure, or any reason where it is believed by the investigator that it is in the best interest of the patient to be terminated from the study. Any administrative or other reasons for withdrawal must be documented and explained to the patient. Any patient who discontinues will be encouraged to return to the study center for a study completion visit.

#### **4.5.3.1 Discontinuation from Study Drug**

Patients may continue to receive treatment with vemurafenib until disease progression (as defined by the investigator, according local institutional standard of care), unacceptable toxicity, or any other discontinuation criterion is met, as follows, whichever occurs first.

- Disease progression as assessed per institutional standards of care
  - Progressive disease during the antecedent protocol. If approval to treat beyond progression was already given in the antecedent protocol, the patient may roll over into the current protocol.
  - Under special circumstances, when it is believed that the patient may clinically benefit from continued therapy with vemurafenib (e.g., in case of mixed progression or progression of single lesion or appearance of a new single lesion), enrollment into this protocol and dosing beyond progression may be considered if it is judged by the investigator, in consultation with the Sponsor, to be in the best interest of the patient. All such cases will require approval of the Sponsor before continuing study drug treatment within this protocol.
- Intolerance of vemurafenib
- If treatment is suspended more than 28 days, the patient should be withdrawn from the study
- Initiation of other cancer medication
- Pregnancy

Patients who discontinue study drug prematurely will be asked to return to the clinic for an end of treatment visit (see Section 4.5.2.4 and Appendix 1). The primary reason for premature study drug discontinuation should be documented on the appropriate eCRF. Patients who discontinue study drug prematurely will not be replaced.

*All patients who discontinue vemurafenib treatment will be followed for safety surveillance per the investigator's discretion.*

Note: New primary melanomas identified as part of the dermatologic risk management plan outlined in Section 4.5.1.9, which are completely excised and without need for additional therapy, do not require patient discontinuation from study treatment.

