### **3.3 END OF STUDY**

The study will end when all enrolled patients have discontinued study treatment and have been followed for safety *assessment until 28 days after the last dose of study drug*, death, withdrawal of consent, loss to follow-up, or if the Sponsor has decided to terminate the study, whichever occurs first.

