#### **4.4.2 Prohibited Therapy**

Use of the following therapies is prohibited during the study (i.e., from 7 days before the initiation of vemurafenib treatment [on Study GO28399] until the end of treatment visit):

- St. John's wort or hyperforin
- Any concomitant therapy intended for the treatment of cancer (approved by health authorities or experimental), including chemotherapy, radiation therapy, immunotherapy, hormonal therapy, biologic therapy, investigational agents, or herbal therapy; certain forms of radiation therapy may be considered for pain palliation following consultation with the medical monitor. Study treatment should be suspended during radiation therapy. Undergoing radiation therapy  $\leq 1$  week prior to first administration of vemurafenib and stereotactic radiotherapy is prohibited.

Patients who require the use of any of these agents will be discontinued from study treatment and followed for safety outcomes for 28 days after the last dose of study treatment or until the initiation of another anti-cancer therapy, whichever comes first. Follow-up for new primary malignancies will continue *per investigator's discretion*.

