#### **4.5.2.4 End of Treatment Visit**

Patients who complete the study or discontinue from the study drug for any reason will be asked to return to the clinic within 28 days after their last dose of vemurafenib or before starting new non-protocol therapy (whichever is earliest) for an end of treatment visit. The visit at which a response assessment showed disease progression will be used as the end of treatment visit. The following assessments will be performed:

- Physical examination (including examination of the eyes, ears, nose, and cardiovascular, dermatological, musculoskeletal, respiratory, gastrointestinal, genitourinary, and neurological systems and the safety surveillance assessment for new primary malignancy including head and neck, anus, and pelvic [for female patients only] examinations)
- Vital signs
- 12-lead ECG (prior to blood samples)
- ECOG Performance Status
- Hematology
- Serum chemistries
- Concomitant medications
- Adverse events

Refer to [Appendix 1](#) for assessments to be performed at the study completion or early termination visit.

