### **5.3.1 Adverse Event Reporting Period**

Investigators will seek information on adverse events at each patient contact. All adverse events, whether reported by the patient or noted by study personnel, will be recorded in the patient's medical record and on the Adverse Event eCRF.

After informed consent has been obtained but prior to initiation of study drug, only serious adverse events caused by a protocol-mandated intervention should be reported (e.g., serious adverse events related to invasive procedures such as biopsies).

After initiation of study drug, all adverse events, regardless of relationship to study drug, will be reported until 28 days after the last dose of study treatment or until initiation of another anti-cancer therapy, whichever comes first.

*Instructions for reporting adverse events that occur after the adverse event reporting period are provided in Section 5.6.*

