- i. A dermatological evaluation will be conducted at baseline, prior to treatment, at Cycles 2 and 3, then every other cycle through Cycle 15. Then, for patients still receiving treatment, a dermatological evaluation will continue to be conducted every third treatment cycle starting at Cycle 18 (i.e., screening and every three cycles per the Cycle 18+ period for patients with  $\geq 17$  cycles of vemurafenib on an antecedent study), and until withdrawal of consent, death, or loss to follow-up (whichever occurs earliest). A window of  $\pm 21$  days from the scheduled study visit (with exception of the baseline evaluation) is allowed for completion of the dermatologic assessments cited above. It is recommended that the examination to be performed by a dermatologist; however, it can also be performed by a qualified physician. All patients will be followed for cuSCC, as well as other new cutaneous neoplasms, until *28 days* after treatment completion, death, withdrawal of consent, or loss to follow-up, whichever occurs first. Patients should see their physicians as needed for any new skin lesions while on the study drug. An unscheduled dermatology examination may be performed at any time during treatment, if clinically indicated. An examination from the antecedent protocol may be utilized as the screening examination for the extension (rollover) protocol if it was conducted within 30 days prior to first dose of vemurafenib on Study GO28399.
- j. Chest CT scans must be performed at baseline, within 30 days before start of study treatment on Study GO28399, and every 6 months (within a window of  $\pm 21$  days) after initiation of treatment until death, withdrawal of consent, loss to follow up or up to *28 days* after study drug discontinuation, whichever occurs first. Available routine chest CT scans (e.g., performed for tumor assessments during the antecedent study period) that fit the required timeline specification can be used for this safety surveillance.
- k. Tumor assessments, including radiological tumor assessments of chest, abdomen, pelvis, and brain, for measuring extent of disease (CT scan is the preferred method) will be done at the discretion of the investigator or per institutional guidelines. An examination from the antecedent protocol may be utilized as the screening examination for the extension (rollover) protocol if it was conducted within 30 days prior to the first dose of vemurafenib.

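### Sections 4.5.3.1 and 4.5.2.5 can be read to end adverse event collection before the mandatory 28 days are over, so the only listed outcome measure may be incompletely ascertained

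*Combined protocol and SAP*

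**What the plan says.** The protocol makes two kinds of statement about the time after a patient stops vemurafenib.

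The first kind fixes a period. Under Section 5.3.1, once dosing has begun, all adverse events are reported whatever their cause, "until 28 days after the last dose of study treatment or until initiation of another anti-cancer therapy, whichever comes first". Sections 4.5.1.6 and 4.5.2.1 set the same period for recording, and Sections 3.1.1, 5.1.2.2 and 5.6 also use 28 days. Section 3.3 says "The study will end when all enrolled patients have discontinued study treatment and have been followed for safety" and continues "assessment until 28 days after the last dose of study drug", with death, withdrawal of consent, loss to follow-up and sponsor termination as alternatives. For new primary invasive malignancies, Section 5.1.2.3 requires reporting up to 28 days after treatment completion. For skin lesions, Appendix 1 note i says "All patients will be followed for cuSCC, as well as other new cutaneous neoplasms, until" that same point, unless death, withdrawal of consent or loss to follow-up comes first.

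The second kind loosens it. Section 4.5.3.1 says "All patients who discontinue vemurafenib treatment will be followed for safety surveillance per the investigator's discretion". Section 4.5.2.5 says that after the study completion visit only serious events judged related are to be reported. Under Section 4.5.2.4 patients "will be asked to return to the clinic within 28 days after their last dose of vemurafenib or before starting new non-protocol therapy", and the visit whose assessment showed progression takes the place of that visit. Appendix 1 has one post-treatment column and schedules no later contact.

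Section 4.4.2, which concerns only patients who need a prohibited therapy, has both elements in sequence. They are "followed for safety outcomes for 28 days after the last dose of study treatment or until the initiation of another anti-cancer therapy", and then "Follow-up for new primary malignancies will continue" at the investigator's discretion.

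**The concern.** Section 4.5.3.1 is where a site looks when a patient stops drug. It applies discretion to every such patient and states no minimum period. Section 4.5.2.5 goes further, because it says which events to report and which not, and it takes effect at a visit whose date can vary over the whole window.

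The study has no efficacy outcome measure. Sections 3.5.2 and 6.3 make the incidence, nature and severity of adverse events the only listed outcome measure, summarised over all patients who received at least one dose. With that denominator, a patient whose post-dose events were not collected counts as a patient without those events. If sites follow different sections, reported incidence is too low by an amount that varies with site practice and with how soon the end of treatment visit took place.

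**Working it through.** There is no figure to reproduce. Section 6 states that there is no formal hypothesis testing, and the sample size is simply the number of patients who roll over. The check is a comparison of texts.

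**Step 1: which visit triggers Section 4.5.2.5?** It refers to the study completion visit, while Section 4.5.2.4 describes the end of treatment visit. Section 4.5.2.4 closes by sending the reader to Appendix 1 for the study completion or early termination visit, and Appendix 1 contains only the end of treatment visit. I therefore take the two as the same visit. This is the natural reading, but the documents do not say so outright.

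**Step 2: can that visit precede Day 28?** Yes. It may take place on any day within 28 days of the last dose. For a patient who stops at progression, the visit that showed progression is used, and that is likely to be close to the last dose.

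**Step 3: what happens to an event after that visit but before Day 28, if no other anti-cancer therapy has started?**

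| Event | Fixed-period rules | Section 4.5.2.5 read literally |
|---|---|---|
| Serious, related | Report (5.3.1) | Report |
| Serious, unrelated | Report (5.3.1, 5.4) | Do not report |
| Non-serious, related or unrelated | Report (5.3.1) | Do not report |
| cuSCC as a non-serious event of special interest | Report whatever the cause (5.1.2.3, 5.4) | Do not report |
| New primary invasive malignancy judged unrelated | Report as serious (5.1.2.3) | Do not report |

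The rules agree only in the first row.

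**Step 4: does Section 4.5.2.5 correct itself?** Its last instruction refers to Sections 5.5 and 5.6. Section 5.6 applies the related-serious rule only after the 28-day reporting period. So Section 4.5.2.5 starts the restriction at the visit, and the section it cites starts it at the end of the period.

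**Step 5: does a narrow reading of Section 4.5.3.1 remove the conflict?** Suppose its discretion covers only surveillance for squamous cell carcinoma and new primaries. Section 5.1.2.3 and Appendix 1 note i fix 28 days for those too, and neither lists the start of another therapy as an end event. The conflict is narrower but remains.

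**The case against.** The strongest reply is that Section 4.5.3.1 says nothing about recording or reporting adverse events, and that every section which does govern adverse event collection fixes 28 days, apart from 4.5.2.5. The protocol mostly uses the term safety surveillance for malignancy examinations. The sentence stands next to a note on new primary melanoma, and the Version 5 rationale lists Section 4.5.3 among the places where the 3- and 6-month visits were removed. The likely intent is that longer-term malignancy surveillance became discretionary. Section 4.5.3.1 also asks patients who stop early to attend an end of treatment visit, at which adverse events are collected.

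Much of this stands. It makes intent fairly clear and limits the point to conflicting text. It does not say when the discretion starts, and it does not touch Section 4.5.2.5.

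A reader might draw three stronger conclusions that the documents do not support:

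- That post-dose events are in fact ascertained selectively. Sections 4.5.1.6, 4.5.2.1 and 5.3.1 remain mandatory, so this is a risk if a site follows the looser sections, not a rule of the protocol. Nothing shows that patients who stop for toxicity would be followed more closely than others.
- That the share of the 28 days left after an early visit, or the drug's half-life, measures the loss. The share comes from the flexible visit window and would be the same without the sentence in 4.5.3.1. Time without a scheduled visit is also not the same as events missed, and the half-life counts no missed event.
- That the end-of-study condition cannot be met. Section 3.3 lists alternatives, including loss to follow-up and sponsor termination.

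**Conclusion.** The point holds as an internal contradiction in current text. Section 4.5.3.1 does not say when its discretion begins, and Section 4.5.2.5 can cut reporting to related serious events while the Section 5.3.1 period is still running. Section 4.5.2.5 is the sharper of the two conflicts. A site following 4.5.2.4, 4.5.2.5 and 4.5.3.1 together could reasonably stop collecting non-serious or unrelated events that Section 5.3.1 requires.

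The consequence is possible incomplete and uneven ascertainment of descriptive adverse event incidence and severity. No test, error rate or sample size is affected. The size cannot be derived: the documents give no distribution of visit dates, no post-dose event rate and no information on which section sites follow.

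The conclusion on Section 4.5.2.5 assumes that the study completion visit is the end of treatment visit. It matters most where that visit is early and no other anti-cancer therapy follows at once. Where one does, the Section 5.3.1 period closes and the overlap shrinks, although the malignancy follow-up in Section 5.1.2.3 and note i does not list that as an end event.

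**What to change.** Reconcile Sections 4.5.3.1 and 4.5.2.5 with Section 5.3.1 in the next amendment:

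- State in both sections that all adverse events are collected for the full Section 5.3.1 period, whatever the date of the end of treatment visit.
- In Section 4.5.3.1, state that the investigator's discretion applies only after that period and does not shorten the 28-day malignancy follow-up in Section 5.1.2.3 and Appendix 1 note i.
- In Section 4.5.2.5, start the related-serious-only rule at the end of the Section 5.3.1 period, as Section 5.6 already does, and use one name for the visit.

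An optional low-cost addition applies where the visit took place early: a telephone check of adverse event status at the end of the period, dated on the eCRF. This closes the gap in scheduled contact, but the reconciliation does not depend on it.

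The cost is a few sentences, a few more adverse event records and, if the check is adopted, one call per patient with an early visit.

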#### **4.5.3.2 Withdrawal from Study**

Every effort should be made to obtain information on patients who withdraw from the study. The primary reason for withdrawal from the study should be documented on the appropriate eCRF. Patients will not be followed for any reason after consent has been withdrawn. Patients who withdraw from the study will not be replaced.

#### **4.5.4 Study and Site Discontinuation**

The Sponsor has the right to terminate this study at any time. Reasons for terminating the study may include but are not limited to the following:

- The incidence or severity of adverse events in this or other studies indicates a potential health hazard to patients.
- Patient enrollment is unsatisfactory.
- All enrolled patients have discontinued study treatment.

The Sponsor will notify the investigator if the study is placed on hold or if the Sponsor decides to discontinue the study or development program.

The Sponsor has the right to replace a site at any time. Reasons for replacing a site may include but are not limited to the following:

- Poor protocol adherence
- Inaccurate or incomplete data recording
- Non-compliance with the International Conference on Harmonisation (ICH) guideline for Good Clinical Practice (GCP)

### **5. ASSESSMENT OF SAFETY**

#### **5.1 SAFETY PLAN**

Measures will be taken to ensure the safety of patients participating in this trial; in particular, the use of inclusion and exclusion criteria and close monitoring of patients.

## **5.1.2 General Plan to Manage Safety Concerns**

### **5.1.2.1 Eligibility Criteria**

Eligibility criteria exclude patients who previously discontinued vemurafenib for any reason in an antecedent protocol or who met an exclusion criterion, as specified in the antecedent study or the extension (rollover) protocol.

### **5.1.2.2 Monitoring**

Safety will be evaluated in this study through the monitoring of all adverse events and targeted laboratory assessments according to NCI CTCAE v4.0. Patients will be monitored on Day 1 of every subsequent cycle and as needed until 28 *days* after the last dose of study treatment or initiation of other anti-cancer therapy, whichever occurs first.

All treatment-emergent adverse events and serious adverse events, whether or not deemed treatment related, will be followed until they resolve or become stabilized, the patient is lost to follow-up or withdraws consent, or it has been determined that the study treatment or participation is not the cause of the adverse event or serious adverse event. General safety assessments will include serial interval histories, physical examinations, and specific laboratory studies including serum chemistries, liver function tests, and blood counts.

All serious adverse events and protocol-defined adverse events of special interest (see Section 5.4.2) will be reported in an expedited fashion.

### **5.1.2.3 Monitoring and Management of Specific Toxicities and Conditions That May Arise with Treatment with Vemurafenib Non-Squamous Cell Carcinoma Skin Toxicity**

The non-SCC skin toxicities observed in patients treated with vemurafenib include rash, pruritus, palmar-plantar erythrodysesthesia, dry skin, and exfoliation. Of these, the most common has been rash (maculopapular or acneiform), which has generally been manageable with supportive care. Skin toxicities other than lesions suspected of being cuSCC will be managed with supportive care according to institutional guidelines as well as by dose interruption/modification, as specified in Section 5.1.2.3.

Mild to severe photosensitivity has been reported in patients who received vemurafenib in clinical studies. All patients should be advised to avoid sun exposure while taking the study drug. Patients should be advised to wear protective clothing and use a broad spectrum UVA/UVB sunscreen and lip balm (sun protection factor  $\geq 30$ ) when outdoors to help protect against sunburn. For photosensitivity Grade  $\geq 2$  (intolerable) adverse reactions, dose modifications will be required (see Section 5.1.2.3).

### **Management and Safety Surveillance for Cutaneous Squamous Cell Carcinoma and New Primary Melanoma**

If a patient develops cuSCC during the study, this information must be collected and reported as a non-serious adverse event of special interest to the Sponsor, whether it is deemed related or unrelated to study drug.

If a patient develops a new primary melanoma during *the* study, this information must be collected and reported as a non-serious adverse event of special interest to the Sponsor, whether it is deemed related or unrelated to study drug. An unscheduled dermatologic examination may be performed during treatment for investigation of any new suspicious skin lesions.

Confirmed cuSCC and/or new primary melanoma should be completely resected and treated according local institutional standard of care. Vemurafenib treatment interruption and/or dose modifications are not recommended (see Section 5.1.2.3).

See Section 4.5.1.9 for more details.

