#### **4.5.1.8 Electrocardiograms**

ECG recordings according local institutional standards will be obtained at each specified timepoint (see [Appendix 1](#)). ECGs for each patient should be obtained from the same machine, whenever possible. To minimize variability, it is important that patients be in a resting position for  $\geq 10$  minutes prior to each ECG evaluation. Body position should be consistently maintained for each ECG evaluation to prevent changes in heart rate. Environmental distractions (e.g., television, radio, conversation) should be avoided during the pre-ECG resting period and during ECG recording. ECGs should be

performed prior to any vital sign measurements and at least 15 minutes prior to blood draws scheduled to be performed on the same day.

For safety monitoring purposes, the investigator or designee must review, sign, and date all ECG tracings. Paper copies will be kept as part of the patient's permanent study file at the site. ECG characteristics, including heart rate, QRS duration, and RR, PR, and QT intervals, will be monitored by the investigator. If the patient experiences a Grade 3 or Grade 4 QT prolongation (according to NCI CTCAE v4.0), the event should be recorded on the eCRF and reported as an expedited non-serious adverse event of special interest, including the QTc value.

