## New Primary Invasive Malignancies

All new primary invasive malignancies will be reported until *28 days* after treatment completion, withdrawal of consent, loss to follow-up, or death, whichever occurs earliest.

If a patient develops a new primary invasive malignancy during or up to *28 days* after study treatment completion, this event must be reported to the Sponsor as a serious adverse event, whether it is deemed related or unrelated to study drug. Thereafter, only new primary malignancies thought to be related to study treatment will be reported as serious adverse events.

Any identified lesion suspected to be a new primary malignancy (including cuSCC, non-cutaneous SCC, and/or new primary melanoma) must be biopsied or excised and sent for pathological examination and should be treated according local institutional standard of care.

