### **5.2.2 Serious Adverse Events (Immediately Reportable to Roche)**

A serious adverse event is any adverse event that meets any of the following criteria:

- Fatal (i.e., the adverse event actually causes or leads to death)
- Life-threatening (i.e., the adverse event, in the view of the investigator, places the patient at immediate risk of death)
  - This does not include any adverse event that, had it occurred in a more severe form or was allowed to continue, might have caused death.
- Requires or prolongs inpatient hospitalization (see Section [5.3.5.10](#))
- Results in persistent or significant disability or incapacity (i.e., the adverse event results in substantial disruption of the patient's ability to conduct normal life functions)
- Congenital anomaly or birth defect in a neonate or infant born to a mother exposed to the study drug
- Significant medical event in the investigator's judgment (e.g., may jeopardize the patient or may require medical or surgical intervention to prevent one of the outcomes listed above)

A new primary invasive malignancy (other than cuSCC or new primary melanoma) or progression or recurrence of a prior invasive malignancy (other than the disease under study) will be characterized as a serious adverse event.

The terms “severe” and “serious” are not synonymous. Severity refers to the intensity of an adverse event (rated as mild, moderate, or severe or according to NCI CTCAE criteria; see Section 5.3.3); the event itself may be of relatively minor medical significance (such as severe headache without any further findings).

Severity and seriousness need to be independently assessed for each adverse event recorded on the eCRF.

Serious adverse events are required to be reported by the investigator to the Sponsor within 24 hours after learning of the event (see Section 5.4.2 for reporting instructions).

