## **5.3 METHODS AND TIMING FOR CAPTURING AND ASSESSING SAFETY PARAMETERS**

The investigator is responsible for ensuring that all adverse events (see Section 5.2.1 for definition) are recorded on the Adverse Event eCRF and reported to the Sponsor in accordance with instructions provided in this section and in Sections 5.4–5.6.

For each adverse event recorded on the Adverse Event eCRF, the investigator will make an assessment of seriousness (see Section 5.2.2 for seriousness criteria), severity (see Section 5.3.3), and causality (see Section 5.3.4).

Adverse events still ongoing or not resolved at the time of enrollment in the extension (rollover) study should be recorded on the Adverse Event eCRF, as specified in the protocol, with the original onset date from the antecedent study.

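### Sections 5.1.2.3 and 4.5.1.8 fix cuSCC, new primary melanoma and Grade 3 or 4 QT prolongation as non-serious, against the per-event seriousness rule of Sections 5.2.2 and 5.3, and the new-malignancy rule omits the Section 5.2.2 exception

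*Combined protocol and SAP*

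**What the plan says.** Three places in the protocol set the class of these events.

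- **Fixed as non-serious.** Section 5.1.2.3, on cutaneous squamous cell carcinoma (cuSCC) and new primary melanoma, states: "If a patient develops cuSCC during the study, this information must be collected and reported as a non-serious adverse event of special interest". The following paragraph uses the same wording for new primary melanoma. Section 4.5.1.8 says that Grade 3 or 4 QT prolongation is to be "reported as an expedited non-serious adverse event of special interest, including the QTc value". None of these sentences has an exception for a case that meets a seriousness criterion.
- **Assessed case by case.** Section 5.2.2 makes any adverse event that meets a listed criterion an SAE and adds: "Severity and seriousness need to be independently assessed for each adverse event recorded on the eCRF". Section 5.3 repeats the duty: "For each adverse event recorded on the Adverse Event eCRF, the investigator will make an assessment of seriousness". Section 5.3.5.10 makes an event that results in hospitalization an SAE, apart from listed exceptions. Section 5.2.2 also has an automatic SAE class, which opens "A new primary invasive malignancy (other than cuSCC or new primary melanoma". Those two lesions are outside the automatic class but remain SAEs if a criterion is met.
- **Fixed as serious.** Section 5.1.2.3, under New Primary Invasive Malignancies, says of any such malignancy during treatment or up to 28 days after it that "this event must be reported to the Sponsor as a serious adverse event, whether it is deemed related or unrelated to study drug". It continues: "Thereafter, only new primary malignancies thought to be related to study treatment will be reported as serious adverse events". The next paragraph, on biopsy, counts cuSCC and new primary melanoma among new primary malignancies.

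Section 5.2.3 lists cuSCC, new primary melanoma and Grade 3 or 4 QTc prolongation as adverse events of special interest (AESIs) without assigning a class. Section 5.3.5.6 lets a liver event be reported in either class.

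**The concern.** A cuSCC that leads to hospitalization cannot be reported as non-serious under Section 5.1.2.3 and as an SAE under Sections 5.2.2 and 5.3.5.10. The same holds for a melanoma, or a QT prolongation, that meets any other criterion when first reported. The new-malignancy text raises the opposite problem: read literally, it makes an invasive cuSCC an SAE even when no criterion is met.

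The incidence of adverse events and SAEs is the study's only outcome measure (Sections 3.5.2 and 6.3). If sites follow different sections, the SAE count depends partly on which section they read. The investigator's seriousness assessment also feeds health-authority reporting (Section 5.7). After the reporting period, Section 5.6 asks only for related SAEs, so there the class decides whether a report is due at all.

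**Working it through.** No figure in the plan bears on this, so the check applies each rule to the same cases.

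| Case | Fixed-class text (5.1.2.3 cuSCC/melanoma; 4.5.1.8 QT) | 5.1.2.3, new primary invasive malignancies | 5.2.2 with 5.3 |
|---|---|---|---|
| Invasive cuSCC or melanoma on treatment, no criterion met | Non-serious AESI | SAE | Not an SAE; AESI |
| Same lesion, a criterion met at first report | Non-serious AESI | SAE | SAE |
| Grade 3 or 4 QT prolongation, no criterion met | Non-serious AESI | Not covered | Not an SAE; AESI |
| Grade 3 or 4 QT prolongation, a criterion met at first report | Non-serious AESI | Not covered | SAE |
| Related cuSCC or melanoma more than 28 days after treatment, no criterion met | Limited to events during the study | SAE, if read with the biopsy paragraph | Not an SAE, so not called for by 5.6 |

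1. Rows 2 and 4 show the main contradiction. The fixed class is wrong exactly when the event is already serious. Row 3 shows that it does no harm otherwise.
2. Row 1 shows the missing exception. The new-malignancy text and Section 5.2.2 disagree on an invasive lesion that meets no criterion.
3. Row 5 shows the mismatch for late cases. The sentence on cases after 28 days drops the restriction to invasive disease. The next paragraph includes both lesions in the term used. Together they make late related cases SAEs, while Section 5.2.2 keeps these lesions out of the automatic class.

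**Size.** For patient-level SAE incidence, the shift would be p × s × u. Here p is the proportion of patients with such an event, s the share whose class depends on the section followed, and u the share of those with no other SAE. For tables by event type, u drops out. Section 1.2.1.5 gives background values of p only: cuSCC about 20% across studies, and new primary melanoma 7/337 = 2.1%. Neither s nor u is given. The Phase III study counted all cuSCC and keratoacanthoma as serious for reporting purposes, so it does not show how many met a criterion on their own. The shift cannot be computed.

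**The case against.** The best defence is that the phrase non-serious AESI names a reporting route. Sections 5.2, 5.4, 5.4.2 and 5.5.2 use it that way, and seriousness must be assessed for every recorded event anyway. Section 5.3.5.3 also requires a persistent event that later becomes serious to be reported within 24 hours and its eCRF entry changed. This narrows the gap to events already serious at first report. It does not close it, because Sections 5.1.2.3 and 4.5.1.8 never say that they name only a route.

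A second defence is that Section 5.2.2 is the definitions section, so its exception carries over to the new-malignancy text. That is a reasonable reading, but the text does not state it. Even if it is accepted, the conflict between the fixed non-serious class and Section 5.2.2 remains.

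Third, the late cases matter less than they might. Appendix 1 follows patients for cuSCC and other new cutaneous neoplasms only until 28 days after treatment, and later follow-up is at the investigator's discretion (Sections 4.4.2 and 4.5.3.1). That limits how many such cases arise but does not reconcile the sentences.

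Three stronger readings are tempting, and the documents do not support them:

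- A reader might infer from the Table 2 footnote that every Grade 4 QT prolongation is an SAE. Table 2 covers events not listed in the CTCAE, and Section 4.5.1.8 grades QT prolongation by the CTCAE.
- A reader might infer that every excised lesion is serious, because Section 5.2.2 mentions events that "may jeopardize the patient or may require medical or surgical intervention to prevent one of the outcomes listed above". That criterion is left to the investigator's judgment, and nothing says that excision alone meets it.
- A reader might infer that the plan is silent on whether late cuSCC and melanoma count as new primary malignancies. The biopsy paragraph includes them. The fault is a mismatch with Section 5.2.2, not silence.

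**Conclusion.** This is an internal contradiction that merits consideration. Followed literally, the fixed class in Sections 5.1.2.3 and 4.5.1.8 misclasses any cuSCC, new primary melanoma or Grade 3 or 4 QT prolongation that is serious at first report. The new-malignancy rule disagrees with Section 5.2.2 in the other direction.

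The size is not derivable and is probably small. Section 1.2.1.5 describes cuSCC as typically managed by simple excision and reports no serious QT prolongation in the Phase II study. Within the reporting period both classes reach the sponsor within 24 hours (Section 5.4), and the sponsor may upgrade (Section 5.7). Section 6 has no hypothesis test, so no error rate or power is affected. A reader might take the 20% cuSCC incidence as the size of the effect. It counts any cuSCC, not those whose class is in dispute, and Section 1.2.1.5 says cuSCC usually appears early in treatment, whereas these patients have already been treated. The judgment that the effect is small assumes that background experience carries over to this rollover population.

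**What to change.** 1. In Section 5.1.2.3 (the cuSCC sentence and the melanoma sentence) and in Section 4.5.1.8, remove the fixed class. Use the open form of Section 5.3.5.6: report as an SAE or as a non-serious AESI, with seriousness assessed per Section 5.2.2.
2. In the first SAE sentence under New Primary Invasive Malignancies, add in brackets: other than cuSCC or new primary melanoma, unless a Section 5.2.2 criterion is met.
3. Reconcile the sentence on cases after 28 days with Sections 5.2.2 and 5.6. State whether it is limited to invasive disease, and whether late related cuSCC and new primary melanoma are to be reported as SAEs. Copying the bracketed exception into this sentence would settle that question without saying so.

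The cost is the wording of five sentences, one in Section 4.5.1.8 and four in Section 5.1.2.3. No assessment, table or analysis is added. Only the third item needs a sponsor decision, because it sets what is reported after the reporting period.
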